6. BIOSPECIMEN COLLECTION (IF APPLICABLE)

Biospecimens will not be collected as part of our study. Thus, specimen preparation, handling and storage are not applicable.

6.1 Specimen preparation, handling, and shipping: $\ensuremath{\mathrm{N/A}}$

6.2 Instruction for specimen preparation, handling and storage: N/A

6.3 Specimen shipment: N/A

6.4 Future use of stored specimens: N/A

7. STUDY PROCEDURES

7.1 Screening Procedures

After confirming that potential study participants meet basic demographic inclusion criteria, patients will be evaluated by a trained Otologist at MEEI. A detailed history will be obtained and a physical exam will be completed. Subjects will also be evaluated for baseline qualitative measures using questionnaires and quantitative measures using audiologic testing.

In accordance with 21 CFR 812.25 (c), we will attempt to match the proportions of women and minorities included in past trials for the indication of CI surgery in patients with SSD. We will also attempt to include an even distribution of patients with regards to age, sex, race and ethnicity as there is no particular population of patients affected by the conditions addressed by our study. However, given the small sample size of our study, it will be difficult to capture all patient demographics.

7.2 Enrollment/Baseline Procedures

All baseline procedures will be completed at the time of screening. This includes qualitative measurement using the Modified Hearing Handicap Inventory, Abbreviated Profile of Hearing Aid Benefit (APHAB), the Speech Spatial and Qualities of Hearing Scale (SSQ) and Quality of Life (SF-36) questionnaires as well as audiologic tests such as Early Speech Perception Testing and Consonant-Nucleus-Consonant testing. The degree to which tinnitus in the non-hearing ear affects the participant's well-being will be assessed using the Tinnitus Handicap Inventory. Auditory Brainstem Response (ABR) will be measured in patients with tinnitus as an additional clinical correlation, conducted for research purposes. Finally, patients will travel to the Binaural Hearing and Speech Lab at the University of Wisconsin – Madison for hearing-in-noise and spatial hearing testing pre- and post-operatively (see below). All costs for airfare, accommodations, meals and a daily stipend will be covered by funding from [name] laboratory.

7.3 Study Drug or Device Procedures

Subjects will undergo pre-operative evaluation for cochlear implant surgery. Those subjects that are appropriate for surgery will undergo a procedure for implantation of the MAESTRO Cochlear Implant system. As per manufacturer protocol, the parameters of the cochlear implant system including adjustment of electrode sensitivities and activation of specific electrodes will be completed at each follow-up visit post-operatively. This process involves adjustment of device parameters by a trained audiologist who subsequently administers audiologic tests to confirm optimal activation of the cochlear implant device.

7.4 Standard of Care Procedures

All audiologic testing and assessments represent the standard of care. Aspects of our study that go beyond routine standard of care are outlined above and in the informed consent.

7.5 Follow-up Procedures

Study participants will have audiologic testing and device activation and adjustment completed at follow-up appointments. These post-operative follow-up appointments will occur at 4 weeks, and at three, six, and twelve months. Timing of these appointments may vary by as much as four weeks prior to or after the planned follow-up date (e.g. between 2-4 months for the 3 month follow-up).

7.6 Unscheduled Visits

Unscheduled visits will be taken in the Otology clinic as needed to address any concerns study participants may have regarding the use of their cochlear implant device.

7.7 Early Termination

Subjects whose participation in the study is terminated early will be replaced through the recruitment of additional subjects through Otology clinic. All subjects may voluntarily withdraw from the study at any time.

7.8 Schedule of Activities (Study Table)

Please see attached.

8. SAFETY AND EFFECTIVENESS ASSESSMENTS

8.1 Safety Assessments

Safety assessments will include questionnaires to assess for complications and frequent postoperative follow-up visits. Inquiries about both major and minor complications will be made and any complications will be recorded. A research assistant will regularly review safety measures every month for all study participants and discuss any safety concerns/adverse outcomes with the investigator.

Any reported safety issues will be carefully recorded and following completion of the study, safety outcomes will be analyzed. Any unanticipated adverse events will be reported to the HSC, FDA, and MED-EL Corporation (see Section 9).

8.2 Effectiveness Assessments

Effectiveness assessments will be completed based on audiologic testing and subjective questionnaires at each follow-up appointment. These will be compared to the subjects' preoperative baseline measures. In particular, primary dependent measures will include:

- Pure Tone Threshold Audiometry
- Sound Localization Testing (University of Wisconsin Madison)
- Speech Perception Measures Consonant-Nucleus-Consonant (CNC) Testing
- Psychophysical Measures
- Tinnitus Assessment Tinnitus Handicap Inventory (THI)
- Subjective Questionnaires Hearing Handicap Inventory, Abbreviated Profile of Hearing Aid Benefit (APHAB) questionnaire, Speech Spatial and Qualities of Hearing Scale (SSQ), and Quality of Life (SF-36) questionnaire

Each CI subject's speech perception ability will be ranked on a continuum of performance by using standardized speech perception tests that document the range of perception abilities. We will use the Consonant-Nucleus-Consonant (CNC) test (House Ear Institute). The CNC open set single-syllable test will be administered and scored both for whole-word and phonemic items. All speech tests will use recorded materials at a level of 65dB HL and will be presented in the soundfield through a speaker to the subject at 0 degree azimuth and calibrated at a set

distance, typically 1 meter. We will test SSD patients in the bilateral condition, using the good ear only and use contralateral masking to eliminate contributions from the good ear to evaluate the implanted ear.

Each subject's spatial hearing ability will be assessed in collaboration with [name] at the University of Wisconsin. Subjects will identify a single word randomly chosen from a set of fifty possibly alternatives and presented from a loudspeaker directly in front of the subjects. Speech intelligibility will be tested by masking sentences co-presented at different spatial configurations. The presentation level of the target speech will be varied in order to generate different signal-to-noise ratios at each condition. We will evaluate implanted SSD patients with the device turned on and off to directly evaluate contribution of the cochlear implant to understanding speech-in-noise.

Recorded test materials, test keys and patient response forms will be collected and documented as part of the study. Number of test items and percentage scores on each test will be documented and included in the data analysis.

All subjective questionnaires will serve as an additional qualitative assessment of hearing and will not be used to directly guide quantitative audiologic testing. Measures from subjective questionnaires will be carefully documented for each subject and included in data analysis. These questionnaires will be completed before the activation appointment and prior to each of the follow-up appointments.

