Cochlear implantation in SSD patients has also resulted in significantly improved sound localization and ability to hear in noise (Kamal et al., 2013). One important study examined SSD patients who were treated with cochlear implantation; the untreated side was either normal or treated with a hearing aid. The data demonstrated that, although there was a significant benefit in speech understanding and subjective quality of sound, sound localization only improved in patients with normal hearing on the opposite side (Vermeire and Van de Heyning, 2009). These findings are consistent with a more recent pilot study, in which three patients with short-term SSD and normal hearing in the other ear received a cochlear implant on the deafened side. These patients all achieved open-set speech recognition, improved sound localization, and improved word recognition in noise (Firszt et al., 2012). Another critical study evaluated SSD patients who had undergone cochlear implantation, comparing use of the cochlear implant to a CROS or BAHA. This study found that cochlear implantation resulted in significant gains with respect to objective sound localization and hearing-in-noise testing relative to the CROS or BAHA device in the same patients. Subjective and quality of life measures were also significantly improved with use of the implant (Arndt et al., 2010). Taken together, early data indicate that cochlear implantation in SSD can result in significant tinnitus suppression, improved sound localization and hearing-in-noise, and better quality of life overall.

2 Our hypotheses are that adult patients with postlingual, single-sided deafness who undergo cochlear implantation will 1) wear the implant full-time, 2) report that the cochlear implant provides benefit, 3) show improvement in speech comprehension in quiet and in background noise, 4) demonstrate an improvement in sound localization, and 5) report a reduction in the frequency and intensity of tinnitus compared to before

surgery. To test these hypotheses, we will formally and systematically test patients both before and after surgery as detailed below.

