2. STUDY OBJECTIVES

2.1 Primary Objective

The primary objective of this study is to better assess the efficacy of cochlear implants in enhancing hearing abilities in patients with single sided deafness. The parameters being assessed include hearing in background noise, sound localization, tinnitus suppression, and overall quality of life. Our study will address several specific aims including:

Aim 1: Determine the audiologic outcomes following CI surgery for single sided deafness.

We will implant ten adult patients with postlingual single sided deafness with the MED-EL MAESTRO CI with Flex 28 electrode array using a round window insertion approach. Intraoperative imaging with a reverse Stenver xray will be performed to confirm proper electrode placement. We will assess sound-field thresholds for the cochlear implant alone and word recognition ability in the monoaural and binaural condition. We will also have patients complete the following questionnaires: 1) Hearing Handicap Inventory for adults, 2) Abbreviated Profile of Hearing Aid Benefit and 3) Speech, Spatial, and Qualities of Hearing Scale (SSQ)(Noble and Gatehouse, 2006) prior to and after implantation to assess subjective benefit outcomes. Finally, we will document the reported frequency of implant use and the use settings of the implant.

Aim 2: Determine the spatial hearing benefits following CI surgery for single sided deafness.

The bilateral benefits of understanding speech-in-noise will be evaluated in collaboration with [name] at the University of Wisconsin. Briefly, subjects will be flown to Madison and undergo spatial hearing testing in [name] lab pre- and post-operatively. Funding from [name] lab will cover all costs for travel, accommodations and meals for the subject and one travel companion. Subjects will be their own control and testing will take place at time points before and after surgery. They will be tested with the acoustic ear alone before the CI surgery. Following CI surgery, testing will be done with the bilateral condition and with the acoustic ear alone. On one task, subjects will identify a single

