10. STATISTICAL METHODS/DATA ANALYSIS

10.1 Primary endpoint(s) or outcome measure(s)

The study has a primary endpoint of one year following cochlear implant surgery for ten study participants. Outcomes measures include audiologic measures and subjective questionnaires as described in previous sections, as well as safety assessments completed throughout the study.

Our previous work has established the importance of these physiological, psychophysical, audiologic tests, questionnaires on efficacy, and safety measures as a comprehensive method for assessing the outcomes of cochlear implant surgery. In particular, the use of these measures will allow us to obtain both objective and subjective data to assess the safety and efficacy of cochlear implant placement in patients with single sided deafness and thereby understand how cochlear implant placement has influenced patients' hearing and quality of life. By comparing our findings and measures to data obtained in other patient populations (such as patients with single sided deafness who do not undergo cochlear implantation), we will better understand whether cochlear implant placement in this patient population has improved safety and efficacy compared to no treatment.

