10.2 Secondary endpoints or outcome measure(s)

The secondary outcome measure of this study is the effect of cochlear implantation on tinnitus suppression in patients with tinnitus in the non-hearing ear. Outcomes will be assessed using the Tinnitus Handicap Inventory and auditory brainstem response testing as previously indicated. Prior studies have indicated that cochlear stimulation via a cochlear implant device can suppress tinnitus. By comparing our findings and measures to data obtained from patients with single sided deafness who do not undergo cochlear implantation, we will better understand the utility of cochlear implantation for tinnitus suppression in this patient population.

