10.3 Sample Size Determination

Our study will recruit ten participants for placement of a MAESTRO Cochlear Implant device with follow-up measurements and assessments for one year post-operatively. Although our study is limited to a small sample size of ten patients, the single subject research design will allow each subject to serve as his or her own control, accommodating heterogeneity of the subjects' backgrounds and providing adequate power to test the major hypotheses. Previous studies have used a similar study design and sample size, with statistically significant findings regarding efficacy and safety of cochlear implants in patients with single sided deafness. Given that single-sided deafness is an experimental indication for cochlear implantation, it is appropriate to assess efficacy in a small cohort prior to recruiting more subjects. This will allow us to avoid unnecessary surgery in patients who may not benefit from this intervention.

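### Section 8.2 labels nine measures primary, but the plan names none to decide effectiveness, sets no multiplicity rule, and gives tinnitus and the questionnaires conflicting status

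*Combined protocol and SAP*

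**What the plan says.** Section 8.2 compares follow-up results with each subject's "preoperative baseline measures" and introduces its list with "In particular, primary dependent measures will include". The six bullets name pure-tone thresholds, sound localization, CNC, psychophysical measures, the Tinnitus Handicap Inventory (THI), and four questionnaires: Hearing Handicap Inventory, APHAB, SSQ and SF-36. The closing paragraph of 8.2 then describes all the questionnaires as an additional, qualitative assessment.

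Section 10.1 states: "The study has a primary endpoint of one year following cochlear implant surgery for ten study participants". On the variables it says only "Outcomes measures include audiologic measures and subjective questionnaires as described in previous sections", together with safety assessments.

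On tinnitus, the primary objective in 2.1 reads: "The parameters being assessed include hearing in background noise, sound localization, tinnitus suppression, and overall quality of life". Section 2.2 places the THI under the secondary objective, and 10.2 says: "The secondary outcome measure of this study is the effect of cochlear implantation on tinnitus suppression".

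Section 10.3 describes the design as "providing adequate power to test the major hypotheses" without saying which hypotheses are the major ones. Section 1.2 lists five without ranking them, beginning "1) wear the implant full-time, 2) report that the cochlear implant provides benefit". Section 10.5 calls for per-subject analysis, descriptive statistics and unnamed non-parametric tests, with p ≤ 0.05 for all statistical analyses.

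**The concern.** A primary endpoint should tell the reader, before the data are seen, which result decides whether the implant works. Here the section headed for that purpose supplies a date, and the section that supplies variables gives nine of them equal rank. With p ≤ 0.05 available to each, one favourable result could be reported as the primary finding, and nobody could tell from the plan whether it was chosen in advance. The conflicting labels widen the choice, because tinnitus and the questionnaires can be counted as primary or not, depending on the section cited.

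Section 10.3 presents the cohort as the step that assesses efficacy before more subjects are recruited. It matters, then, which result that assessment rests on.

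**Working it through.** **The plan's own figure.** The sample size of ten is said to give adequate power. It cannot be reproduced, because no effect size, standard deviation, power, sidedness or deciding variable is stated.

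**How many measures are primary?** This depends on which section governs:
- Nine: every instrument named in the 8.2 bullets.
- Six: each bullet counted once.
- Four: thresholds, localization, CNC and psychophysical measures. These remain if the closing paragraph of 8.2 governs the questionnaires and 10.2 governs tinnitus.

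These counts allow one result per measure or bullet. CNC is scored for words and for phonemes in more than one listening condition (8.2), and localization is tested in quiet and at several signal-to-noise ratios (2.1, Aim 2).

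**Status of the disputed measures.**

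| | Primary | Not primary |
|---|---|---|
| Tinnitus / THI | 2.1; 8.2 list | 2.2; 10.2 |
| Questionnaires | 8.2 list | 8.2 closing paragraph |

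Section 10.1 includes the questionnaires among the outcome measures, and 2.1 includes quality of life, so the closing paragraph of 8.2 does not settle their status.

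**Illustrative false-positive rate.** Assumptions, none of them stated in the plan: one group-level exact two-sided signed-rank test per measure at one year, ten pairs, no true change.
- Attained size of one test at n = 10: 0.0488, or 0.0244 in each direction.
- For m independent measures, the chance of at least one false positive is 1 − (1 − 0.0488)^m. Counting only results in the beneficial direction, it is 1 − (1 − 0.0244)^m.

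| Measures | Either direction | Beneficial only |
|---|---|---|
| 1 | 4.9% | 2.4% |
| 4 | 18% | 9% |
| 6 | 26% | 14% |
| 9 | 36% | 20% |

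The documents give no correlations between measures. Simulation with equally correlated normal changes (200,000 runs per setting) gives, at correlation 0.7 and 0.9:
- nine measures: 22% and 14% (beneficial only, 11% and 7%);
- six measures: 18% and 12% (beneficial only, 9% and 6%).

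**Would Holm be workable?** The first step is 0.05/9 = 0.0056 for nine measures and 0.05/8 = 0.0063 for eight. The smallest two-sided signed-rank p is 2/2^n: 0.0020 with ten pairs, 0.0039 with nine and 0.0078 with eight. Either first step can be met with ten or nine pairs but not with eight.

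**The case against.** The strongest reply is that this is a ten-subject, single-subject design, analysed subject by subject and largely descriptively, so group-level error control does not apply. That is a fair objection to giving the percentages much weight: the plan names no signed-rank test, and the analysed number may differ from ten because withdrawn subjects are replaced (5.2) while their data are kept (10.4). It does not dispose of the point, since the same plan sets a significance level for all analyses and claims power to test hypotheses. Section 10.5 also requires deviations to be described and justified. That is a partial safeguard, but a deviation from an undefined choice cannot be detected.

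Some stronger readings are tempting but not supported:
- A reader might take 36% as the trial's false-positive rate. It needs the widest count, independence and an assumed test. If the later label for the questionnaires and 10.2 govern, the figure is about 18%.
- A reader might infer that no comparator is given. Section 8.2 states the preoperative baseline, and 2.1 and 8.2 already plan postoperative contrasts: bilateral versus acoustic ear alone, and device on versus off. What is missing is which one decides.
- A reader might conclude that the THI must be secondary. In 2.2 it is the leading measure of tinnitus relief, within the secondary objective; 2.1 and hypothesis 5 in 1.2 pull the other way. The documents conflict and do not settle the direction.
- A reader might add inflation from the interim analyses. Section 10.7 does not say that they test efficacy, so none is claimed.

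**Conclusion.** The point holds and should be corrected. No measure is designated to decide effectiveness, no testing order or multiplicity rule is set, and tinnitus and the questionnaires each carry contradictory labels. This follows from the text alone and does not depend on any calculation.

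The size is uncertain. Under the assumptions listed, the chance of at least one false-positive primary result is 18% to 36% for four to nine independent measures. It is 14% for nine measures correlated at 0.9, and roughly half the independent figures if only benefit counts. The small first cohort lowers the stakes, but the claim of adequate power for major hypotheses means that it does not remove them.

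**What to change.** 1. In 8.2 and 10.1, name one primary measure, chosen by the sponsor, with its score, listening condition, contrast and visit. The contrast may be against the preoperative baseline or one of the postoperative contrasts already planned in 2.1 and 8.2. Test it once at two-sided 0.05 with a named group-level paired non-parametric test, added to the per-subject description. Alternatively, list several primary measures and apply Holm across the final list.
2. In 10.5, limit the p ≤ 0.05 sentence to that test or Holm family. Report all other measures as secondary or exploratory with 95% confidence intervals.
3. Give tinnitus and the THI one status across 2.1, 2.2, 8.2 and 10.2, and the questionnaires one status across 2.1, both places in 8.2, and 10.1. For tinnitus, the simplest route is to demote it in 2.1 and the THI in the 8.2 list, but the sponsor may choose the other direction.
4. In 10.3, tie the major hypotheses to the named primary measure, and drop the claim of adequate power unless a calculation supports it.
5. If localization is chosen, reconcile the Wisconsin visit, which 3.1 places after twelve months post-activation, with the one year after surgery in 10.1.

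The cost is wording only, with no extra subjects or visits. The sponsor gives up unadjusted significance claims on non-primary measures. Holm over eight or nine measures could not reach its first step with only eight complete pairs, so a shorter primary list tolerates missed visits better.

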9. ADVERSE EVENT RECORDING AND REPORTING

9.1 Recording Requirements

Research subjects will be routinely questioned about adverse events at study follow-up visits.

> RECORDING REQUIREMENT

All observed or volunteered adverse events (serious or non-serious) and abnormal test findings, regardless of suspected causal relationship to the study device will be recorded in the subjects' case histories (source data, case report form). For all adverse events, sufficient information will be obtained to permit 1) an adequate determination of the outcome of the event (i.e., whether the event should be classified as a serious adverse event) and; 2) an assessment of the casual relationship between the adverse event and the cochlear implant system.

Adverse events or abnormal test findings felt to be associated with the cochlear implant system will be followed until the event (or its sequel) or the abnormal test finding resolves or stabilizes at a level acceptable to the Sponsor-Investigator.

> ABNORMAL TEST FINDINGS

An abnormal test finding will be classified as an adverse event if one or more of the following criteria are met:

- The test finding is accompanied by clinical symptoms
- The test finding necessitates additional diagnostic evaluation(s) or medical/surgical intervention, including significant additional concomitant drug treatment or other therapy
- The test finding leads to discontinuation of subject participation in the clinical research study
- The test finding is considered an adverse event by the Sponsor-Investigator of the IND or IDE application

> CASUALTY AND SEVERITY ASSESMENT

The Sponsor-Investigator of the IND or IDE application will promptly review documented adverse events and abnormal test findings to determine 1) if the abnormal test finding should be classified as an adverse event; 2) if there is a reasonable possibility that the adverse event was caused by the MAESTRO cochlear implant system; and 3) if the adverse event meets the criteria for a serious adverse event.

If the Sponsor-Investigator's final determination of causality is "unknown and of questionable relationship to the study device", the adverse event will be classified as associated with the use of the cochlear implant system for reporting purposes. If the Sponsor-Investigator's final determination of causality is "unknown but not related to the study device," this determination and the rationale for the determination will be documented in the respective subject's case history (case report form).

